### **6.1.2.2 Maintenance phase (Visit 5 - Visit 9) - amended**

Subject should take the riociguat morning dose at home as usual, except of Visit 5, where the morning dose will be taken at the hospital. The following procedures will be performed during the maintenance period:

- Record concomitant medication incl. concomitant PAH specific medication
- Perform physical examination (incl. height, weight, vital signs and at Visit 9 only, pubertal assessment using Tanner scale)
- Collect PK sample (Visit 5 only, for details see [Table 0–2](#))
- Pregnancy test for females of childbearing potential
- Dispense study medication
  - Instruct how to take study drug
- Check adverse events including adverse events of special interest
- Check the systolic BP monitoring form provided by the patients at the visit, if applicable
- Check drug accountability
- Determine WHO functional class (Visit 9 only)
- Perform echocardiogram (Visit 9 only)
- Perform electrocardiogram (Visit 9 only)
- Perform 6MWD (Visit 9 only)
- Collect NT-proBNP or BNP (Visit 9 only; when both tests are available, NT-proBNP should be chosen over BNP and the same test should be performed at every required visit)
- X-ray of left hand for determination of bone age (Visit 9 only)
- Child Health Questionnaire (SF-10 and PedsQL Generic Core Scales self-report) (Visit 9 only)
- Taste assessment questionnaire (Visit 9 only)
- Obtain laboratory parameters (AST, ALT, BUN, creatinine, GGT, UA, T-Bil, Alb, Na, K, Ca, P, and CBC) at Visits 5 and 9 as well as record the same parameters when

obtained as medically required according to a local package insert of bosentan or other ERA, or medical practice at the study site at any time

- In case RHC is conducted based on medical reasons during the study, record RHC parameters to eCRF

*(Note: The Section was modified according to Amendment 3, see Sections 17.1.1.8, 17.1.1.14, and 17.1.1.16. The Section was modified according to Amendment 5, see Sections 17.2.1.1 and 17.2.1.2. The section was modified according to Amendment 6, see Sections 17.3.1.2, 17.3.1.3, and 17.3.1.6. This section was modified according to Amendment 9, see Section 17.4.1.13.)*

### **6.1.3 End-of-treatment visit - amended**

For all subjects dropping-off the protocol at any time after V1 and before V9, an end-of-treatment visit has to be performed.

The same procedures as at Visit 9 will be performed with the exception of the x-ray of left hand.

In case RHC is conducted based on medical reasons during the study, record RHC parameters to eCRF.

*(Note: The Section was modified according to Amendment 3, see Section 17.1.1.16. The Section was modified according to Amendment 5, see Section 17.2.1.2. This section was modified according to Amendment 9, see Section 17.4.1.13.)*

### **6.1.4 Safety follow-up visit - amended**

For all subjects stopping study medication either at the end of treatment or prematurely discontinuing the study at any time, a follow-up visit 60 days ( $\pm 8$  days) after last study medication intake has to be performed.

For subjects directly proceeding with treatment in the long-term extension phase, a safety follow-up visit 60 days (+8 days) will be scheduled either at the end of optional LTE phase, when patient's transition to approved and commercially available riociguat in the respective country is possible, or when prematurely discontinuing LTE phase at any time.

The following procedures will be performed:

- Record concomitant medication incl. concomitant PAH specific medication
- Perform physical examination (incl. height, weight and vital signs)
- Pregnancy test for females of childbearing potential
- Check adverse events including adverse events of special interest
- Record laboratory parameters (AST, ALT, BUN, creatinine, GGT, UA, T-Bil, Alb, Na, K, Ca, P, and CBC) to eCRF when obtained as medically required according to a local package insert of bosentan or other ERA, or medical practice at the study site at any time
- In case RHC is conducted based on medical reasons during the study, record RHC parameters to eCRF

*(Note: The safety follow up visit added to concern all subjects as well as the wording was changed according to Amendment 3, see Section 17.1.1.4. The Section was modified*

*according to Amendment 5, see Sections 17.2.1.1 and 17.2.1.2. The section was modified according to Amendment 6, see Section 17.3.1.2.)*

### **6.1.5 Unscheduled visit - amended**

If deemed necessary, it is at the investigator's discretion to arrange additional visits. The following procedures will be performed:

- Record concomitant medication incl. concomitant PAH specific medication
- Perform physical examination (incl. height, weight and vital signs)
- Dispense study medication (if required)
  - Instruct how to take study drug
- Check adverse events including adverse events of special interest
- Update eCRF
- Record laboratory parameters (AST, ALT, BUN, creatinine, GGT, UA, T-Bil, Alb, Na, K, Ca, P, and CBC) to eCRF when obtained as medically required according to a local package insert of bosentan or other ERA, or medical practice at the study site at any time
- In case RHC is conducted based on medical reasons during the study, record RHC parameters to eCRF

*(Note: The Section was modified according to Amendment 5, see Sections 17.2.1.1 and 17.2.1.2. The Section was modified according to Amendment 6, see Section 17.3.1.2.)*

### **6.1.6 Optional long-term extension phase (until adulthood or approval in the indication and commercial availability) - amended**

Children who require treatment with riociguat for more than 24 weeks will be offered participation in the optional extension phase. Subjects who become  $\geq 18$  years of age will continue to receive their individually optimal dose of riociguat (drug) from the clinical supply for up to 6 months to allow the transition to commercial product to complete as locally applicable.

The following procedures will be performed:

#### **Every 3 ( $\pm$ 14 days) months**

- Record concomitant medication incl. concomitant PAH specific medication
- Pregnancy test for females of childbearing potential  
Pregnancy testing is to be performed in 4-weekly intervals starting at Visit 1 until 4 weeks after the patient stops intake of study drug. If the interval falls on a visit date pregnancy testing is to be performed locally while at all other dates the patient is to perform a urine dipstick test at home. The results are to be documented in the eCRF and in the patient file. The result of every home urine pregnancy test should be actively requested by the site as soon as the test is due. The patient must report a positive result to the site without delay. The results are to be documented in the eCRF and in the patient file in a timely manner. It is not acceptable to obtain the result only at the next scheduled visit at the site.

- Perform physical examination (In the long term extension phase the physical examination includes monitoring of growth velocity in addition to the. height, weight and vital signs)
- Dispense study medication
  - Instruct how to take study drug
- Check drug accountability
- Check adverse events including adverse events of special interest
- Exploratory efficacy (6MWD test, WHO FC, NT-proBNP or BNP[when both tests are available, NT-pro-BNP should be chosen over BNP and the same test should be performed at every required visit], QoL [SF-10 and PedsQL Generic Core Scales self-report], echocardiography, TTCW)
- If needed and to reduce burden, 6MWD test and echocardiography can be performed at every second visit in LTE at the discretion of the investigator
- Record laboratory parameters (AST, ALT, BUN, creatinine, GGT, UA, T-Bil, Alb, Na, K, Ca, P, and CBC) to eCRF when obtained as medically required according to a local package insert of bosentan or other ERA, or medical practice at the study site at any time
- In case RHC is conducted based on medical reasons during the study, record RHC parameters to eCRF
- X-ray of the left hand will be performed every 12 months until growth plates are closed
- Pubertal assessment using Tanner scale will be performed every 12 months
- Perform the Child Health-related Questionnaire (SF-10) and PedsQL. The age version used must match with subject's actual age at time of completing the questionnaire.

*(Note: The wording was modified according to Amendment 3, see Sections 17.1.1.1 and 17.1.1.14. The Section was modified according to Amendment 5, see Sections 17.2.1.1 and 17.2.1.2. The Section was modified according to Amendment 6, see Sections 17.3.1.2, 17.3.1.3, and 17.3.1.6. The Section was modified according to Amendment 9, see Section.17.4.1.13.)*

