## Study flow chart - amended

Table 0–1: Flow chart - amended

	Screening	Main study treatment period - 24 weeks									Unscheduled visit	End of treatment visit l	Safety follow-up 60 ± 8 days	Optional Long-term extension phase	Safety follow up visit 60 +8 days after optional LTE
		Individual titration phase (8 weeks)				Maintenance phase (16 weeks)									
Visit	V0	V1 g	V2	V3	V4	V5	V6 k	V7	V8 k	V9				Every 3 months (± 14 days)	
Week f	Day -14 to -1	0	2	4	6	8	12	16	20	24					
Informed consent/assent	•														
In-/exclusion criteria	•	•													
Demographics	•														
Medical history	•														
Concomitant medication		•	•	•	•	•	•	•	•	•	•	•	•	•	•
Concomitant PAH specific medication	•	•	•	•	•	•	•	•	•	•	•	•	•	•	•
Physical examination m	•	• d	•	•	•	•	•	•	•	•	•	•	•	• h	•
Obtain lab test	• i					•				•		•			
Pregnancy test a	•	•		•		•	•	•	•	•		•	•	•	•
Dispense study medication		•	•	•	•	•	•	•	•	•	(•)			•	
Instruct how to take study drug		•	•	•	•	•	•	•	•	•	(•)			•	

Table 0–1: Flow chart - amended

	Screening	Main study treatment period - 24 weeks									Unscheduled visit	End of treatment visit l	Safety follow-up 60 ± 8 days	Optional Long-term extension phase	Safety follow up visit 60 +8 days after optional LTE
		Individual titration phase (8 weeks)				Maintenance phase (16 weeks)									
Visit	V0	V1 g	V2	V3	V4	V5	V6 k	V7	V8 k	V9				Every 3 months (± 14 days)	
Week f	Day -14 to -1	0	2	4	6	8	12	16	20	24					
Provide study guidelines		•													
Vital signs	•	• d	•	•	•	•	•	•	•	•	•	•	•	•	•
ECG	•	• d								•		•			
Echocardiogram		•								•		•	•		
RHC data o	• o														
WHO functional class		•								•		•	•		
6MWD		•								•		•	•		
NT-proBNP or BNP p		•								•		•	•		
Left hand x-ray		• j								•			• e		
Adverse events n	•	•	•	•	•	•	•	•	•	•	•	•	•	•	•
Drug accountability			•	•	•	•	•	•	•	•		•	•		
PK blood sample b		•		•		•									
Child Health Questionnaire (SF-10 and PedsQL)	•									•		•	•		

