**Table 0-1: Flow chart - amended**

- a Urine or serum pregnancy test for women of childbearing potential, in the LTE pregnancy testing is to be performed in 4-weekly interval; also actively request the results of the home urinary pregnancy test as soon as this test is due
- b A minimum volume of 1.0 mL per sample is needed. Accurate adherence to time points is essential and has to be documented, see [Table 0–2](#)
- c Scale of physical development in children and adolescents
- d At Visit 1 blood pressure, heart rate and ECG pre-dose, 2 and 4 hours after first dose (see [Table 0–2](#))
- e Every 12 months until growth velocity is plateauing and growth plates are closed (see section [6.1.6](#))
- f ±2 days for Visits 1 to 4, ±4 days for Visit 5, ±5 days for Visits 6 to 9
- g Visit 1 is considered the baseline visit
- h Including monitoring of growth velocity
- i Obtain blood samples if AST and ALT, creatinine, BUN, GGT, UA, T-Bil, Alb, Na, K, Ca, P, and CBC are not available within 30 days prior to Visit 0. Record the same laboratory parameters to eCRF when obtained as medically required according to a local package insert of bosentan or other ERAs, or medical practice at the study site at any time.

- j If no historical data (not older than 30 days) of x-ray is available
- k Home visits (only at week 12 and/or 20 of maintenance phase) at the discretion and responsibility of the investigator
- l For subjects dropping off the protocol at any time after V1 and before V9
- m Including height and weight
- n Including AEs of special interest
- o In case RHC has been performed for a study subject before enrollment, record most recent RHC parameters to the eCRF on V0 (timing of RHC not limited to the period of Day -14 to -1). Additionally, if RHC is conducted on medical reasons during the study, the RHC data should be recorded to the eCRF.
- p When both tests are available, NT-proBNP should be chosen over BNP and the same test should be performed at every required visit

*(Note: The table was modified according to protocol Amendment 3, see Sections 17.1.1.1, 17.1.1.15. The table was modified according to Amendment 5, see Sections 17.2.1.1 and 17.2.1.2. The table and footnotes were modified according to Amendment 6, see Sections 17.3.1.2, 17.3.1.3, 17.3.1.6, 17.3.1.7, and 17.3.1.8. The table was modified according to Amendment 9, see Sections 17.4.1.8, 17.4.1.12, and 17.4.2.4.)*

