### 3.1 Study description - amended

After providing written informed consent and assent (if applicable) subjects will undergo a screening evaluation to determine their eligibility. Eligible subjects – once on stable background treatment with PAH medications (ERA and/or PCA) - will start body-weight adjusted individual dose titration (IDT) regimen as described in section 5.1.1. After the individual titration phase of maximum of 8 weeks, subjects will enter the 16-week maintenance phase. The last dose administered at Visit 4 will be regarded as individual optimal dose and subject will receive that treatment during the maintenance phase.

Subjects of the older age cohort ( $\geq 12$  to  $< 18$  years) will be treated first. After 5 patients of this age cohort have reached their optimal dose and received this dose until assessment of their first control x-ray of left hand at week 24, an independent Data Monitoring Committee (DMC) will give recommendations to the Steering Committee (SC) whether to continue with enrolment in this age cohort and open enrollment in the subsequent lower age cohort ( $\geq 6$  to  $< 12$  years).

Children who require treatment with riociguat for more than 24 weeks will be offered participation in an extension study and continuation until market approval of riociguat for the

pediatric population or until they are 18 years of age (whatever comes first). Subjects reaching adulthood can be transitioned to commercially-available Adempas.

The primary objective is the evaluation of safety and tolerability as well as the pharmacokinetic properties of riociguat in the pediatric population. The DMC will monitor the subjects' safety on an ongoing basis and give recommendations to the SC.

For all subjects, visits are scheduled at regular time points (see [Table 0-1](#)). Subjects who prematurely discontinue study drug or do not consent to participate in the long-term extension phase will be seen at the safety follow-up visit. During all contacts, the treatment and clinical course of the subject will be evaluated. Subjects with suspected safety concerns (for safety outcomes see section [6.2](#)) will undergo confirmatory testing as per standard of care. Blood samples for PK will be taken at defined time points (see [Table 0-2](#)).

The reason why subjects did not pass the screen of in- and exclusion criteria after obtaining informed consent/child assent will be documented.

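### The pregnancy test due 4 weeks after the last dose is set only in the extension section (6.1.6); the flow chart, 6.1.3 and 6.1.4 do not list it, so a girl who leaves after Visit 9 may next be tested at day 52 to 68.

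*Protocol*

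**What the plan says.** Section 6.1.6 gives the frequency and the end point of testing: "Pregnancy testing is to be performed in 4-weekly intervals starting at Visit 1 until 4 weeks after the patient stops intake of study drug". On dates without a visit the test is a home urine dipstick. The site must ask for the result when it falls due and record it in the eCRF: "It is not acceptable to obtain the result only at the next scheduled visit at the site". All of this stands under the 3-monthly procedures of the optional extension.

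Footnote a of Table 0-1 carries the interval in these words: "in the LTE pregnancy testing is to be performed in 4-weekly interval". The pregnancy-test row of the flow chart marks Visits 0, 1, 3 and 5 to 9, the end-of-treatment visit, the safety follow-up, the extension and the follow-up after the extension.

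For those leaving the main study:

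- Section 3.1 says that subjects who stop early or "do not consent to participate in the long-term extension phase will be seen at the safety follow-up visit".
- Section 6.1.3 on the end-of-treatment visit says: "The same procedures as at Visit 9 will be performed with the exception of the x-ray of left hand". That gives one pregnancy test, at that visit.
- Section 6.1.4 covers everyone who comes off drug ("For all subjects stopping study medication either at the end of treatment or prematurely discontinuing the study at any time") and includes one pregnancy test, at the visit the flow chart heads "Safety follow-up 60 ± 8 days".

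None of these places mentions a test 4 weeks after the last dose or points to 6.1.6. Inclusion criterion 7 (section 4.2) ends required contraception at that same 4-week point, with no distinction between main-study and extension leavers.

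**The concern.** One part of the protocol sets a safety test, and the parts a site would use when closing out a main-study patient do not show it. A site with a girl who has finished Visit 9 and is not entering the extension has no evident reason to open the extension section. If it follows the flow chart and 6.1.4, nothing further is known about pregnancy until the 60-day visit. A pregnancy that began on riociguat or shortly after could then be found weeks later than 6.1.6 intends.

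The protocol treats this monitoring as important. Section 8.9 makes non-compliance with pregnancy testing a reason for withdrawal, and 8.10 puts pregnancy reports on SAE timelines.

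Either reading needs a correction. If the rule is for everyone, the main-study schedule leaves out a required test. If it is for the extension only, its starting point of Visit 1 is wrong, and main-study leavers are monitored less closely than extension leavers without a stated reason.

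**Working it through.** **Inputs**

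- Final test under 6.1.6: 4 weeks after the last dose.
- Safety follow-up: 60 ± 8 days after last intake (6.1.4, flow chart, SAP 4.2).
- Main-study test visits: Visits 1, 3, 5, 6, 7, 8 and 9, at weeks 0, 4, 8, 12, 16, 20 and 24 (flow chart).
- Visit windows: footnote f, plus or minus "2 days for Visits 1 to 4, ±4 days for Visit 5, ±5 days for Visits 6 to 9".

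**Step 1: on-treatment testing.** Successive tests are 4 weeks (28 days) apart throughout, so the main-study schedule already meets the 4-weekly rule. Only the test after the last dose is in question.

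**Step 2: the test 6.1.6 sets.** 4 × 7 = day 28 after the last dose.

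**Step 3: the next test the main-study schedule lists.** Earliest 60 − 8 = day 52 (52/7 = 7.4 weeks); latest 60 + 8 = day 68 (68/7 = 9.7 weeks).

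**Step 4: the difference.** 52 − 28 = 24 days; 68 − 28 = 40 days.

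**Step 5: comparison with on-treatment spacing.** The longest gap the windows allow between two on-treatment tests is 28 + 5 + 5 = 38 days (Visits 6 to 9, windows used in opposite directions). The post-treatment gap is longer by 52 − 38 = 14 to 68 − 38 = 30 days. This compares test spacing only; it does not measure exposure to drug.

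**Step 6: who is affected.**

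| Path | Next listed test after the last dose |
|---|---|
| Completes Visit 9, does not enter the extension | Day 52 to 68 |
| Stops early, end-of-treatment visit, stays in follow-up, no further planned visits | Day 52 to 68, if the end-of-treatment visit falls at or soon after the last dose |
| Stops at week 12, keeps planned visits (8.9) | Week 16: (16 − 12) × 7 = day 28 |
| Stops at week 22, keeps Visit 9 | Week 24: (24 − 22) × 7 = day 14, then day 52 to 68 |
| Refuses further data collection (8.9) | None; no wording change would reach her |

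The first row is the clear case. In the third row the day-28 test happens anyway, at its nominal date.

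**The case against.** The strongest reply is that the test is already required. The 6.1.6 sentence starts at Visit 1 and ends 4 weeks after the patient stops drug, and the method, follow-up and recording are all given there. On this view the fix only repeats the rule elsewhere. That is right about the literal meaning, and it is why the point concerns scope and placement rather than a missing requirement. It does not help a site that works from the flow chart and the section for the visit at hand.

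A reader might infer that footnote a confines the rule to the extension. The words do not support that: they speak of the extension but do not say only. The extension column has 3-monthly visits and so needs a note about more frequent tests; the main-study columns, already 4-weekly, do not. Nor does silence in 6.1.4 show that main-study leavers are excluded. That section covers extension leavers too and is equally silent for them, although 6.1.6 plainly applies to them. A day-28 dipstick also falls on no visit, so one would not expect it in a list of visit procedures.

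A reader might also infer that a health authority asked for this test in main-study leavers. The Amendment 12 log says only that an authority requested the testing frequency. Its description as an amendment about extension details is background and cannot settle the scope of the current text.

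Finally, the effect is small. The girl is tested at Visit 9 or end of treatment and again at day 52 to 68, and contraception is required up to the 4-week point. This stands, and it limits how much weight the point can bear.

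**Conclusion.** The inconsistency is real and modest. Section 6.1.6 sets a day-28 test that read literally covers everyone, while a site following the flow chart, 6.1.3 and 6.1.4 would not schedule it for a girl who completes Visit 9 without entering the extension. Her next listed test is at day 52 to 68, 24 to 40 days after the one 6.1.6 sets. The change should be made because the schedule as laid out gives weaker monitoring than the protocol's own rule.

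The consequence is at most delayed detection. A reader might infer a missed reporting deadline, but 8.6 counts from the investigator's awareness and 8.10 adopts the same timelines. No statistical result changes: SAP 6.4.3 only lists pregnancy tests.

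The figures assume that the last dose falls at about Visit 9 or, for early leavers, that the end-of-treatment visit falls at or soon after the last dose (6.1.3 gives no timing). That a site would skip the test is an inference from where the text stands. The documents do not give the number of girls affected.

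**What to change.** State in footnote a and in 6.1.4, with a cross-reference in 6.1.3, that the 6.1.6 rule applies to every female of childbearing potential who stops study drug, in the main study or the extension. When no scheduled test falls 4 weeks after the last dose, she does a home urine dipstick, handed out at Visit 9 or the end-of-treatment visit, or has a test at the site. The site actively requests the result when it is due and records it in the eCRF, as 6.1.6 already requires for home tests.

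Keep the test at the 60-day safety follow-up, because a negative result at day 28 does not rule out a very recent conception.

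The first test after Visit 9 then moves from day 52 to 68 to about day 28. The cost is one dipstick and one site contact per leaver, plus protocol wording; no visit is added and the SAP does not change.

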## 6.2 Safety outcomes - amended

During the course of the study treatment-emergent adverse events (TEAEs), ECGs, bone age x-ray of left hand, laboratory tests, vital signs, body weight and frequency of premature discontinuations will be assessed.

The primary safety outcome is described as:

- The change from baseline (V1, Day 0) to the end of treatment (V9, week 24) of:
  - Heart rate
  - Blood pressure

- Bone age x-ray of left hand
- Laboratory parameters (see description in respective section below)
- The assessment of:
  - Incidence of treatment-emergent adverse event
  - Incidence of treatment-emergent serious adverse events

Other safety outcomes are the changes from baseline (V1, Day 0) to the end of treatment (V9, week 24) of:

- ECG parameters

